18.17 Clinical Monitoring

Monitoring of the study site will be conducted on a regular basis using a combination of NIDA-contracted monitors and node Quality Assurance (QA) staff. Investigators will host periodic visits by both the NIDA-contracted monitors and local QA site managers; the purpose of which is to encourage and assess compliance with GCP requirements and to document the integrity of the trial progress. The national and local monitors will audit the following items, but not exclusively: regulatory documents, case report forms, Informed Consent Forms, and any corresponding source documents for every participant. Monitors will have the opportunity and ability to review any study-associated document or file.

NIDA-contracted monitors will assess whether submitted data are accurate and in agreement with source documentation and will also review regulatory/essential documents such as correspondence with the IRB. Areas of particular concern will be participant Informed Consent Forms, protocol adherence, reported safety events and corresponding assessments, study drug accountability, and principal investigator oversight and involvement in the trial. Reports will be prepared following the visit and forwarded to the site principal investigator, the lead investigator and NIDA CCTN.

Qualified node personnel will provide site management and monitoring for each site during the trial. This will take place as specified by the local protocol team, node PI, or full Lead Team and

will occur as often as needed to help prevent, detect, and correct problems at the study sites. Node (QA) staff will audit source documentation, including all Informed Consent and HIPAA forms (if applicable). Node QA staff will verify that study procedures are being properly followed and that site staff is trained and able to conduct the protocol appropriately. If the node QA staff's review of study documentation indicates that additional training of study personnel is needed, node QA staff will undertake or arrange for that training. Details of the contract, node QA, and data monitoring are found in the study monitoring plan.

18.18 Study Documentation

Study documentation includes all case report forms, workbooks/worksheets, source documents, monitoring logs and appointment schedules, sponsor-investigator correspondence, signed protocol and amendments, Ethics Review Committee or Institutional Review Board correspondence and approved current and previous consent forms and signed participant consent forms.

Source documents include all recordings of observations or notations of clinical activities and all reports and records necessary for the evaluation and reconstruction of the clinical research study. The original recording of an observation should be retained as the source document. If the original recording of an observation is the electronic record, that will be considered the source.

19.0 SAFETY MONITORING

19.1 Data and Safety Monitoring Board (DSMB)

This study will utilize the CTN DSMB to oversee ongoing trial progress to assure protection of participants' safety while maintaining that the study's scientific goals are being met. The CTN DSMB is responsible for conducting periodic reviews of accumulating safety and efficacy data. It will determine whether there is support for continuation of the trial, evidence that study procedures should be changed, or if the trial should be halted (for safety, efficacy, or recruitment or performance reasons). This process is intended to assure the IRBs, sponsor, and investigators that participants are provided with an accurate and ongoing risk evaluation when participating in CTN research trials.

Monitoring will begin with the initial review of the protocol during the study development process and continue throughout the study with meetings at least annually. Recommendations and reports from these reviews will be distributed to the site lead investigator for submission to their IRB.

19.2 Protocol Deviations Reporting and Management

Any departure from procedures or requirements outlined in the protocol will be classified as protocol deviations. A protocol deviation is an action (or inaction) that alone may or may not affect the scientific soundness of the investigation or seriously affect the safety, rights, or welfare of a study participant. In some cases, a protocol deviation may compromise participant safety, participant rights, inclusion/exclusion criteria or the integrity of study data and is cause for corrective action to resolve the departure and to prevent re-occurrence. Protocol deviations will be monitored at each site for (1) significance, (2) frequency, and (3) impact on the study objectives, to ensure that site performance does not compromise the integrity of the trial. The decision about whether a deviation from the protocol will be designated as minor or major will be made by the Clinical Coordinating Center (CCC) in conjunction with the protocol's Lead Investigator(s). The consequences will be specified and participating sites will be informed.

All protocol deviations will be recorded in the Electronic Data Capture (EDC) system via the Protocol Deviation CRF. The CCC, DSC, and the Lead Investigator must be contacted immediately if an unqualified or ineligible participant is randomized into the study.

Additionally, each site is responsible for reviewing the IRB of record's (and their local IRB's, if applicable) definition of a protocol deviation or violation and understanding which events need to be reported. Sites must recognize that the CTN and IRB definition of a reportable event may differ and act accordingly in following all reporting requirements for both entities. Sites must also recognize that operating under an IRB Authorization Agreement may not excuse them from reporting Protocol Deviations to their local IRBs. Sites are expected to communicate with their IRB as necessary, according to local guidelines.

19.3 Adverse Events (AEs)

The Lead Investigator may appoint a study clinician (MD, DO, NP or PA) for this study, who will review or provide consultation for each serious adverse event as needed. These reviews will include an assessment of the severity and causality of the event to the study intervention (drug or therapy) or other study procedures. The study clinician will also provide advice for decisions to exclude, refer, or withdraw participants as required. In addition, NIDA will assign a centralized Medical Monitor to this protocol to independently review the safety data, present it to the DSMB for periodic review, and provide PIs a Safety Letter when necessary for submission to IRBs for

regulatory compliance. The Medical Monitor will determine which safety events require expedited reporting to NIDA, the DSMB, pharmaceutical/distributors, and regulatory authorities. This will include events that are serious, related, and unexpected. The study staff will be trained to monitor for and report Adverse Events and Serious Adverse Events.

19.3.1 Adverse Events

For the purposes of this study, mild (Grade 1) and unrelated Adverse Events will not require reporting in the data system. All adverse events will be tracked on a manual (paper only) Adverse Event Log, regardless of severity, seriousness, relatedness, or expectedness.

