7.4 Special Populations to Consider

This study is likely to enroll persons involved in the criminal justice system who are receiving HIV care at participating sites. The study will not recruit persons incarcerated/detained in a correctional facility or currently considered "prisoners" by local or state laws, but will not exclude parolees or probationers. At screening, prisoner status will be assessed using a streamlined

assessment based on the definition of a prisoner in 45 CFR 46.303(c). Throughout the study, prisoner status will be documented on the Criminal Justice case report form (CRF).

Those participants who become incarcerated during the course of their involvement with this study will continue to be followed to ensure safety and data integrity. All study interventions (XR-NTX or TAU) will be discontinued while the participant is incarcerated. If necessary for safety and with the permission of the participant, correctional facility officials will be informed of study participation. When possible, participants will be contacted to complete questionnaires and surveys, which would include safety checks. These visits can occur over the telephone or as in-person visits, whichever is more appropriate for the local research site and the correctional facilities' policies. The visits will only occur if confidentiality can be maintained. This generally assumes that in-person visits will be done in private rooms and that recording equipment (regardless of type of visit) can be turned off or destroyed. No biospecimens will be collected (blood or urine) during any visit that occurs with an incarcerated prisoner. If necessary, specific documents for incarcerated participants will be developed and approved by the IRB of record. All local guidelines will be followed, including any required reporting to the IRB or other institution when a participant becomes incarcerated. Despite the use of a central IRB for this study, local IRBs may be notified if a participant becomes incarcerated. Appropriate progress notes will be written to ensure complete documentation of any interaction with an incarcerated participant, specifically mentioning confidentiality procedures.

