9.2.2 Medical Management (when applicable)

Study clinicians will be trained in medical management (MM). MM is a brief counseling intervention delivered by non-addiction medical providers to improve response to medication-assisted addiction treatments delivered in medical settings [129] [130]. It has augmented care for medication-assisted treatment of alcohol dependence with acamprosate and oral naltrexone in the COMBINE study [131], integration of XR-NTX treatment of alcohol dependence in primary care settings [36], and integration of BUP/NX for treatment of opioid dependence in primary care [132]. Since MM is meant to facilitate medication-assisted addiction treatment, it will be performed only for participants offered medication-assisted treatment in the HIV clinic (e.g., participants with opioid use disorders randomized to XR-NTX and TAU participants receiving clinic-based buprenorphine/naloxone or methadone for opioid use disorder). TAU participants referred for off-site methadone maintenance or buprenorphine/naloxone will not receive MM since medical

oversight is the responsibility of the treating provider. TAU participants who receive non-medication-assisted treatments such as 12-step groups or psychosocial counseling will not receive MM. During brief MM sessions, study clinicians will review recent drug and alcohol use, recommend abstinence, review medication side effects, and encourage adherence to medication-assisted treatment and participation in clinic and/or community support groups.

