9.7 Blinding

CTN-0067 is an unblinded study.

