17.13 Safety Analysis

Adverse events (AEs), including serious adverse events (SAEs), will be summarized by body system and preferred term using MedDRA (The Medical Dictionary for Regulatory Activities). Adverse events will be presented in two ways: (1) the number and proportion of participants experiencing at least one incidence of each event will be presented overall and by treatment group; and (2) a table displaying the total number of each event will be given overall and by treatment group. Listings of serious adverse events will be given, sorted by treatment, body system, and preferred term. Detail in these listings will include severity, relationship to study drug, and action taken as available. Treatment arm differences will be monitored by the DSMB.

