23.6.1 Guidelines for Determining Causality

The study medical clinician will use the following question when assessing causality of an adverse event to study drug/intervention where an affirmative answer designates the event as a suspected adverse reaction: Is there a reasonable possibility that the study drug/intervention caused the event?

Please note that for the purposes of this protocol, events assessed to be mild (Grade 1) and unrelated, though reportable on the manual adverse event tracking log, are not reportable in the electronic data capture system.

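### Grade 1 adverse events enter the data system only if an unblinded clinician calls them related, yet Section 17.13 pools them into by-arm tables; mild-event counts can differ between arms without a true difference

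*Combined protocol and SAP*

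**What the plan says.** **Entry rule.** Section 19.3.1 says that "mild (Grade 1) and unrelated Adverse Events will not require reporting in the data system". Section 23.6.1 repeats the rule more firmly: such events "are not reportable in the electronic data capture system". Section 23.4 confines the AE form to reportable events. Section 19.3.1 also requires a paper log of every adverse event, whatever its grade or cause.

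**Who decides, and against what.** Section 23.6.1 gives the causality judgement to the study medical clinician, using one question: "Is there a reasonable possibility that the study drug/intervention caused the event". Section 9.7 says "CTN-0067 is an unblinded study". For known toxicities, Section 19.4 points to the XR-NTX package insert and to nothing else.

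**Analysis.** Section 17.13 plans two by-arm displays. One counts participants who had each event at least once. For the other, "a table displaying the total number of each event will be given overall and by treatment group". Neither is limited by grade or relatedness, and the paper log is not named as a source. The section adds that the DSMB monitors differences between arms.

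**The concern.** Whether a mild event is counted depends on a judgement made after randomization by someone who knows the treatment. That judgement has more to work with in one arm than in the other.

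In XR-NTX there is a single study-supplied drug with a package insert, and Section 16.4 tells clinicians that it can cause nausea lasting a few hours. Such an episode fits the Grade 1 definition in Section 23.6 (under 48 hours). In TAU, Section 9.2.2 allows agonist treatment off-site under another provider, or counselling and 12-step groups with no medication. No guidance says when a TAU event counts as related. The same mild nausea could be entered in one arm and left on paper in the other.

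At stake is the reading of the by-arm AE tables, by the DSMB during the trial and by readers afterwards. A gap in mild events could be created or hidden by the entry rule, and nothing in the tables would show it.

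**Working it through.** The documents give no adverse-event rate and no relatedness rate, so there is no planned figure to reproduce. The check has two parts.

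**1. Does the filter reach the tables?**
- Grade 1 and unrelated: paper log only (19.3.1, 23.6.1).
- Grade 1 and related: AE form (23.4).
- Grade 2 or higher: not caught by this filter, related or not.
- Tables in 17.13: no grade or relatedness limit, so filtered and unfiltered events are added together.

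The wording of 19.3.1 alone might leave room for voluntary entry; 23.6.1 closes that reading.

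**2. What could the filter do to the counts?** With the same true proportion *m* of participants having a Grade 1 event in both arms,

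recorded proportion = *m* × P(called related | arm).

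The only input from the documents is 175 per arm (Section 17.1). Assume *m* = 40%; all attribution rates are also assumptions.

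| Called related, XR-NTX / TAU | Recorded XR-NTX | Recorded TAU | Difference |
|---|---|---|---|
| 30% / 30% | 12% (21) | 12% (21) | 0 |
| 30% / 20% | 12% (21) | 8% (14) | +4 points |
| 30% / 10% | 12% (21) | 4% (7) | +8 points |
| 50% / 10% | 20% (35) | 4% (7) | +16 points |
| 10% / 30% | 4% (7) | 12% (21) | −8 points |

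Example: 0.40 × 0.30 = 0.12, and 175 × 0.12 = 21. With *m* from 20% to 60% at 30% / 10%, the recorded proportions run from 6% versus 2% to 18% versus 6%.

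**Dilution in an any-event row.** Suppose 15% of each arm also has a Grade 2+ event, independently. At *m* = 40% and 30% / 10%:
- XR-NTX: 1 − 0.85 × (1 − 0.12) = 25.2%
- TAU: 1 − 0.85 × (1 − 0.04) = 18.4%
- Gap: 6.8 points, ratio 1.37

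**Non-initiation.** In the pilot, 5 of 12 participants with opioid use disorder assigned to XR-NTX (42%) started within 4 weeks (Section 4.3). If only starters' events could be called related, the 30% / 10% case becomes 0.40 × 0.42 × 0.30 = 5.0% against 4%, a gap of about 1 point. A wider assumption of 25% to 75% called related in XR-NTX and 0% to 10% in TAU gives:
- without this adjustment, 10% to 30% against 0% to 4%, a gap of 6 to 30 points;
- with it, 4.2% to 12.6% against 0% to 4%, a gap of 0.2 to 12.6 points.

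**After the change.** Where the true proportions are equal, entering all Grade 1 events, or leaving Grade 1 out of the comparison, makes this filter's contribution zero.

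**The case against.** **TAU events can be called related.** Section 7.4 states: "All study interventions (XR-NTX or TAU) will be discontinued while the participant is incarcerated". Section 16.0 lists TAU as a study condition, and Section 19.3 judges causality against the intervention whether drug or therapy. Adverse events are solicited from everyone at each visit (15.1), and Section 9.2.2 has clinicians review side effects with TAU participants who receive clinic-based agonist treatment. This stands. A reader might infer that the rule builds in a false XR-NTX excess because TAU events are never entered; the documents do not support that.

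**The size is unknown.** This also stands. The illustrative gaps rest on assumed rates and shrink sharply if many XR-NTX participants never start. The pilot figure is not a forecast, however: the trial uses a modified induction to raise initiation (4.3) and allows a start up to week 20 (9.1.9), and detoxification events might themselves be called related.

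**Some arm differences are real.** TAU participants receive no study injection, so more injection pain under XR-NTX would be no artefact. Injection-site reactions and precipitated withdrawal also have their own records (13.7, 15.4).

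**The consequences are limited.** Section 17.13 is descriptive, with no test and no adverse-event stopping rule. Grade 1 events are mild and short, the primary endpoint is untouched, and a Medical Monitor reviews events for trends (24.2.2). This limits the weight of the point but does not make the mild-event counts comparable.

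**Grade 2+ is not wholly clean.** Section 19.5 sends events tied to HIV complications, addiction treatment or a detoxification stay to study-specific forms, whatever their grade. Detoxification is part of XR-NTX induction (9.2.3.1), so this exclusion need not be neutral between arms. A reader might infer that a Grade 2+ table compares like with like without qualification; it does not, and the fix has to allow for this.

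**Conclusion.** The point holds in a limited form. Recorded Grade 1 events are selected by an unblinded judgement of relatedness, with a toxicity reference for one arm and no attribution guidance for the other. Section 17.13 mixes them with events that did not pass through that selection. Followed as written, the plan can show an arm difference in mild events where none exists, or conceal one that does.

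An XR-NTX excess is the more plausible direction, but neither direction nor size is established. With *m* = 40%, the table's assumed attribution rates give anything from 8 points against TAU to 16 points against XR-NTX, and zero when attribution is equal. These figures show that the mechanism can matter; they are not estimates.

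A reader might also conclude that mild events cannot be compared at all in this trial. That goes too far, because the paper log should hold every event in both arms. The by-arm tables need correcting; the primary analysis is unaffected.

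**What to change.** In Section 17.13:

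1. Base the between-arm AE tables and the DSMB arm comparison on Grade 2+ and serious events.
2. Show related Grade 1 events in a separate descriptive table covering both arms, labelled as filtered by relatedness and not comparable between arms.
3. Next to the AE tables, show by arm the events that Section 19.5 sends to study-specific forms, or footnote their exclusion.
4. If a mild-event comparison is wanted, take it from the paper log that Section 19.3.1 already requires, entered for both arms.

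Items 1 to 3 are SAP wording and need no new data collection, since severity and causality are already assessed (23.5). The downside is that mild events are not compared between arms unless the log is entered; item 4 costs that data entry.

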19.3.2 Serious Adverse Events

For the purpose of this study, the following events will not be reported as an SAE, but will be recorded on study specific forms in the data system.

- 1) Detox admissions (documented instead on the DTX form).**
- 2) Admission for labor and delivery (documented instead on the Confirmed Pregnancy and Outcomes form).**
- 3) Admission for elective or pre-planned surgery.**

The Lead Node will report all other SAEs on the Serious Adverse Event form in the data system. Sites must determine if local IRBs will require annual or other SAE reporting.

19.4 Known Potential Toxicities of Study Drug/Intervention

Refer to the package insert for XR-NTX.

19.5 Known Potential Adverse Events Related to the Underlying Clinical Condition and/or Study Populations

Each of the participating research sites has established practices for managing medical and psychiatric emergencies, and the study staff will continue to utilize these procedures. Treatment providers at each research site will be responsible for monitoring participants for possible clinical deterioration or other problems, and for implementing appropriate courses of action.

As this population will have significant ongoing health and substance use issues, events related to complications of HIV, substance use treatment or admission for substance detoxification will be captured on study-specific forms and not duplicitely reported as an adverse or serious adverse event. All hospitalizations for other (non-HIV, non-substance-use related) medical, surgical and psychological reasons and deaths will be reported on AE/SAE forms. These data will still be included in the reports to the DSMB at the regular meetings.

20.0 DATA SAFETY MANAGEMENT AND PROCEDURES

20.1 Design and Development

This protocol will utilize a centralized Data and Statistics Center (DSC). The DSC will be responsible for development of the electronic case report forms (eCRFs), development and validation of the clinical study database, ensuring data integrity, and training site and participating node staff on applicable data management procedures. Advantage eClinical, a web- based distributed data entry system, will be implemented. This system will be developed to ensure that guidelines and regulations surrounding the use of computerized systems used in clinical trials are upheld. The remainder of this section provides an overview of the data management plan associated with this protocol.

20.2 Site Responsibilities

The data management responsibilities of each individual site will be specified by the DSC and outlined in the Advantage eClinical User's Guide.

20.3 Data Center Responsibilities

The DSC will 1) develop a data management plan and will conduct data management activities in accordance with that plan, 2) provide final guided source documents and eCRFs for the collection of all data required by the study, 3) develop data dictionaries for each eCRF that will comprehensively define each data element, 4) conduct ongoing data monitoring activities on study data from all participating sites, 5) monitor any preliminary analysis data cleaning activities as needed, and 6) rigorously monitor final study data cleaning.

